10.1.1 Adverse Events Leading to Discontinuation of Study Drug

A summary of incidence rates (frequencies and percentages) of NEAEs leading to discontinuation of study drug by SOC and preferred term will be prepared for the Safety population.

A data listing of AEs leading to discontinuation of study drug will also be provided, displaying details of the event(s) captured on the CRF.

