# 11. DEFINITIONS, RECORDING, AND REPORTING OF ADVERSE EVENTS AND PREGNANCY

## 11.1. Definition of Adverse Events

According to International Council on Harmonisation (ICH) guidance E2A, Clinical Safety Data Management: Definitions and Standards for Expedited Reporting, an AE is any untoward medical occurrence in a patient or clinical investigation patient administered a pharmaceutical product and which is not necessarily required to have a causal relationship with this treatment. An AE can therefore be any unfavorable and unintended sign (including an abnormal laboratory finding, for example), symptom, or disease temporally associated with the use of a medicinal product, whether or not considered related to the medicinal product.

A newly-emergent adverse event (NEAE) is defined as any new AE that starts after the patient's baseline visit for P306, or any ongoing AE that was first reported during the lead-in study or 12-

week open-label extension study and which then exhibits an increase in severity, frequency or relationship after the patient's participation in P306 has begun. NEAEs and "All AEs" will be tallied by System Organ Class (SOC) and preferred terms. AEs that are ongoing at the time of the patient's baseline visit for P306 but which resolve, or persist without change in severity, frequency or relationship to study drug during the extension study, will be included in the tally of all AEs.

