# 12.1. Evaluation of Safety

Safety data will be summarized as a single treatment group receiving 1 or more doses of TNX-102 SL (patients that have taken only 1 tablet of TNX-102 SL will be included).

Safety will be assessed by the monitoring and recording of AEs, clinical laboratory tests, vital signs, visual examination of the oral cavity findings, the monitoring of suicidality using the Columbia C-SSRS scale, and patient-rated assessments of depressive symptomology (BDI-II) and PTSD symptomology (PCL-S).

AEs will be coded using the MedDRA and will be summarized overall and by preferred term and SOC. AEs will also be summarized by severity and relationship to study drug. SAEs and AEs leading to discontinuation of study drug will also be summarized.

Actual values and changes from the extension study baseline values for clinical laboratory test results and vital sign measurements will be summarized at endpoint using descriptive statistics (n, mean, standard deviation (SD), median, minimum, and maximum). Laboratory values will be displayed in the data listings along with corresponding normal ranges, and those that are outside the normal range will be flagged.

Based on the C-SSRS results, the frequency and severity of suicidal ideation and behavior will be tabulated at each time point. The number of patients with baseline and treatment-emergent suicidal ideation and/or suicidal behavior or self-injurious behavior, based on the C-SSRS, will be summarized by treatment group.

All data gathered will be listed by patient and parameter, and clinically significant abnormalities should be recorded as AEs. AEs of special interest indicating potential abuse and dependency will be evaluated and summarized as described in the Statistical Analysis Plan.

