10.1 Adverse Events

All AEs will be coded using MedDRA, version 19.0.

Newly emergent adverse events (NEAEs) are defined as any new AE that started after the patient's first dose of study drug in Study TNX-CY-P306, or any unresolved AE first reported in Study TNX-CY-P301 or Study TNX-CY-P303 that exhibited an increase in severity, frequency or relationship after the patient's participation in Study TNX-CY-P306 had begun. For clarity, adverse events are classified as NEAEs based on a negative response to the CRF question "Did the AE start prior to the first dose?".

An AE summary table will be presented for the following:

• NEAEs by severity

Protocol: TNX-CY-P306 Page 21 of 36

Final v1.0

• NEAEs leading to study drug discontinuation

- NEAEs by relationship
- SAEs
- Oral Cavity NEAEs

Summaries of incidence rates (frequencies and percentages) of individual AEs by MedDRA SOC and preferred term will be prepared. Such summaries will be displayed for all NEAEs, NEAEs by maximum severity, NEAEs by strongest relationship to study drug, and oral cavity NEAEs. Incidence of oral cavity NEAEs will be presented by category and preferred term, rather than SOC and preferred term.

Each participant will be counted only once within each summation level (SOC; preferred term). If a participant experiences more than one NEAE within each summation level only, the NEAE with the strongest relationship or the maximum severity, as appropriate, will be included in the summaries of relationship and severity.

Oral cavity adverse events will be defined by a custom MedDRA query (CMQ). These events will be further divided into 4 categories, as follows: 1) Sensory 2) Discomfort 3) Irritation/inflammation and 4) Lesions. Each category will be defined by a CMQ.

Additionally, a summary of the Oral Cavity AE characteristics will be presented; this includes information such as temporal proximity to the dose, duration and whether the AE was present the following morning. For purposes of this summary, only oral cavity NEAEs with the response "Yes" to the CRF question "Is AE in oral cavity"? will be included.

NEAEs pertaining to abuse potential will be reported by SOC and preferred term, and displayed in tabular format. Terms to be included may be found in Appendix 3.

In the AE data listings, all AEs collected in study TNX-CY-P306 will be displayed. AEs that are newly-emergent will be flagged.

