10.1.2 Serious Adverse Events

A summary of incidence rates (frequencies and percentages) of newly-emergent SAEs by SOC and preferred term will be prepared for the Safety Population. A data listing of all SAEs will also be provided, displaying details of the event(s) captured on the CRF.

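### The P306 tables of AEs leading to discontinuation and of SAEs omit carried-over AEs that do not qualify as newly emergent, which is narrower than the protocol and not declared in SAP 13

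*SAP*

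**What the plan says.** Protocol 12.1 states that "SAEs and AEs leading to discontinuation of study drug will also be summarized", with no condition on when the AE began. Protocol 11.1 separates NEAEs from all AEs and promises tallies of both by system organ class (SOC) and preferred term (PT). AEs ongoing at the P306 baseline that resolve, or that "persist without change in severity, frequency or relationship to study drug during the extension study", go into the all-AE tally and not the NEAE tally.

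The SAP narrows this.

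- **SAP 10.1, overview table.** The discontinuation row is limited to NEAEs. The SAE row carries no such limit.
- **SAP 10.1.1.** The incidence table covers "NEAEs leading to discontinuation of study drug by SOC and preferred term".
- **SAP 10.1.2.** The plan reads "A summary of incidence rates (frequencies and percentages) of newly-emergent SAEs by SOC and preferred term will be prepared for the Safety Population".
- **SAP 10.1, definition.** An unresolved AE from P301 or P303 is an NEAE if it "exhibited an increase in severity, frequency or relationship after the patient's participation in Study TNX-CY-P306 had begun".
- **SAP 10.1, clarification.** The next sentence says that "adverse events are classified as NEAEs based on a negative response to the CRF question", the question being whether the AE began before the first dose.

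The all-AE tally does not appear in the SAP. SAP 13, which records changes from the planned analysis, mentions only the numbering of study days.

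**The concern.** Stopping drug in P306 and becoming serious in P306 are outcomes of the P306 treatment period, whenever the AE began. A filter on onset or worsening suits a count of new AEs. It suits a count of these outcomes less well, because an AE can persist at the same grade until the patient gives up the drug.

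This matters in an extension study. Long-term safety is the primary objective, and some patients enter after about 24 weeks on drug (the 64-week maximum in protocol 6.1 less the 40 weeks of P306). A tolerated AE that eventually makes a patient stop is part of what the study is meant to measure.

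There is also a consistency risk. The P306 discontinuation table can disagree with the withdrawal table in SAP 8.1, which counts withdrawals by reason without regard to AE onset. The SAE table in 10.1.2 can disagree with the unqualified SAE row in 10.1.

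**Working it through.** The plan gives no figure to reproduce, so the check is a comparison of texts.

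**Step 1: are the two outcomes NEAE triggers?** No. SAP 10.1 and protocol 11.1 name three triggers for a carried-over AE: severity, frequency and relationship. Protocol 11.2.2 explains that seriousness is a different thing from severity. An AE can therefore become serious, or lead to stopping, with none of the three triggers met.

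**Step 2: do the definition and the CRF rule agree?** No. The definition admits a carried-over AE that worsens. The CRF rule admits only AEs that began after the first dose. A carried-over AE began before it, so the literal rule excludes it even if it worsened.

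**Step 3: which planned incidence tables count an AE that leads to stopping, or becomes serious, in P306?** The last column uses the SAP 12.2 rules. For patients on TNX-102 SL in P301, any AE in the P303 or P306 database counts unless its recorded start precedes P301 treatment. For patients on placebo in P301, AEs from P301 are disregarded and only those newly emergent in P303 or P306 count.

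| Type of AE | 10.1.1 / 10.1.2, written definition | 10.1.1 / 10.1.2, CRF rule | 12.2 long-term tables |
|---|---|---|---|
| Begins in P306 after first dose | Counted | Counted | Counted |
| Carried over, worsens on a trigger | Counted | Omitted | Counted, but for a P301-onset AE in a P301-placebo patient only if the written definition governs |
| Carried over unchanged, TNX-102 SL in P301 | Omitted | Omitted | Counted, unless it began before P301 treatment |
| Carried over unchanged, placebo in P301, newly emergent in P303 | Omitted | Omitted | Counted |
| Carried over unchanged, placebo in P301, onset in P301 | Omitted | Omitted | Omitted |

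The last row is not empty by design. Protocol 6.2 assigns all patients to TNX-102 SL whatever their P301 arm, and Track B takes in patients who received placebo in P301.

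**Step 4: are the data available?** Yes. Protocol 9.1.5 has ongoing AEs transcribed at Visit 1, and the listings in SAP 10.1.1 and 10.1.2 are not restricted to newly emergent events.

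**Step 5: scale.** If *k* patients have the outcome in P306 and *m* of them have it only through an omitted AE, the table shows *k* − *m*, a relative shortfall of *m*/*k*. The documents give neither number. Each omitted patient lowers the tabulated incidence by 1/200 = 0.5 percentage points at the enrolment cap in protocol 6.2, or by 1/100 = 1.0 point if 100 patients are treated (an assumed figure).

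**The case against.** The strongest reply is that the SAP divides its reporting on purpose: Section 10 covers P306 and Section 12 is cumulative. SAP 12.2 plans SOC/PT tables of serious AEs and of AEs leading to discontinuation in the P306 Safety Population. Those tables recover most carried-over AEs in the patients with the longest prior exposure. The main group left out, P301-onset AEs in placebo patients, began before any TNX-102 SL, and leaving them out is a normal treatment-emergence convention. SAP 8.1 already gives withdrawal percentages by reason, and protocol 9.6 names an AE as a possible reason. The overview table has an unqualified SAE row, and both listings are unrestricted. Protocol 12 leaves the description of analyses to the SAP, and the wording of 12.1 does not say that every AE must be included. The protocol synopsis also treats AEs that worsen after entry as NEAEs, which could be read to cover escalation to a serious event.

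Much of this stands, and it rules out three readings that a reader might infer.

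- *Every carried-over AE that leads to stopping or becomes serious is left out.* Under the written definition, one that worsens on a trigger is counted. The blanket exclusion follows only from the literal CRF rule.
- *These events disappear from the report.* They remain in the listings, and most are in the 12.2 tables.
- *Discontinuation is understated by some stated percentage.* The documents give no counts from which to derive one.

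The reply does not remove the point. The 12.2 tables do not correct the P306 tables, and their serious-AE counts span three studies. SAP 8.1 has no SOC or PT detail and uses all participants with data rather than the Safety Population. Listings give no incidence. The synopsis wording on worsening is not what SAP 10.1 puts into practice. A SAP may narrow the protocol, but SAP 13 is where it should say so.

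**Conclusion.** The point holds in limited form. The P306 SOC/PT tables in SAP 10.1.1 and 10.1.2, and the discontinuation row in 10.1, omit carried-over AEs that lead to stopping or become serious without a rise in severity, frequency or relationship. If the CRF rule is applied literally, they omit all carried-over AEs. This is narrower than the plain wording of protocol 12.1 and is undeclared.

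Across all planned AE incidence tables, the remaining gap is mainly P301-onset AEs in P301-placebo patients. Any error in the P306 tables runs towards lower reported incidence, but its size is unknown. It depends on how many AEs were ongoing at entry, how many of those led to stopping or became serious, and which NEAE rule the programmer follows. The conclusion rests on reading protocol 12.1 as unrestricted, which its contrast with the NEAE and all-AE tallies in 11.1 supports.

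**What to change.** 1. In SAP 10.1 and 10.1.1, tabulate all AEs leading to study drug discontinuation in P306, whatever their onset, with the NEAE subset in a second column.
2. In SAP 10.1.2, tabulate all AEs that are serious on or after the first P306 dose, whatever their onset, again with the newly emergent subset alongside.
3. Reconcile the CRF-question rule in SAP 10.1 with the written NEAE definition, so that a carried-over AE that worsens is classified in one way only.
4. If the restriction is kept instead, declare it in SAP 13 and point the reader to the 12.2 tables.

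The cost is a few sentences in the SAP and one extra column in two tables, using data already collected. The downside is that the reported rates may be slightly less favourable.

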10.1.2 Serious Adverse Events

A summary of incidence rates (frequencies and percentages) of newly-emergent SAEs by SOC and preferred term will be prepared for the Safety Population. A data listing of all SAEs will also be provided, displaying details of the event(s) captured on the CRF.

10.1.3 Deaths

A listing of deaths will also be provided for the Safety Population.

Protocol: TNX-CY-P306 Page 22 of 36

Final v1.0

10.2 Clinical Laboratory Evaluations

Laboratory data include analyses for Chemistry and Hematology and will be summarized by visit for the Safety Population. Descriptive summaries of actual values and change from baseline will be presented by study visit. 95% confidence intervals will be presented for change from baseline for each visit. ET data will be analyzed with the closest visit that does not have a valid assessment value.

Laboratory values will be displayed in the data listings and those that are outside the normal range ("H" or "L") will be flagged, along with corresponding normal ranges. Values pre-defined as potentially clinically significant ("HH" or "LL") will also be flagged. For each laboratory analysis, shifts in assessments of abnormality from baseline to each scheduled time point will be presented in shift tables.

A by-participant listing of all clinical laboratory data will also be provided.

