## 9.3. Visits 3, 4, and 5 (Weeks 7, 16, and 28)

These visits are conducted after 7, 16, and 28 weeks ( $\pm$  7 days) of treatment respectively. The following assessments and procedures are to be conducted at each of these visits in the following general order:

- Collect returned study medication from patient and perform drug accountability
- Assess study drug compliance
- Assess for changes in concomitant medications
- Assess for occurrence of AEs

if any oral AEs have been reported (other than numbness, tingling or bitter taste), perform and document an examination of the oral cavity

- Have the patient complete the "baseline" PCL-S (Visit 5 only)
- Have the patient complete the PROMIS-Sleep Disturbance Scale and the SDS.
   Review each scale for completeness once done.
- Have the patient complete the BDI-II
- Conduct the C-SSRS after reviewing the results of the BDI-II
- Vital signs and weight

- Draw blood for clinical laboratory tests (Visit 5 only)
- Urine pregnancy test (for women of child-bearing potential)
- Inspect the oral cavity and document findings, if any (Visit 5 only)
- Conduct the CGI-I, using the P306 baseline visit as comparison
- Dispense 4 new bottles of TNX-102 SL tablets at Week 7 (Visit 3). At Weeks 16 (Visit 4) and 28 (Visit 5), dispense 5 new bottles.

Review patient instructions regarding drug dosing and storage, and schedule appointment for next clinic visit.

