## 9.6. Early Termination (ET)

In accordance with the Declaration of Helsinki, patients have the right to withdraw from the study at any time for any reason, and they will be advised of this right. The investigator and Tonix also have the right to remove patients from the study. Specific reasons for removal of a patient from the study could include, but are not limited to:

- An AE
- An illness that, in the judgment of the investigator or Tonix, might invalidate the study results or place the patient at risk
- The request of the patient, investigator, or Tonix, whether for administrative or other reasons
- Pregnancy

Patients who wish to terminate their participation in the study should be instructed to come to the clinic for an Early Termination Visit. The purpose of the Early Termination visit is to obtain critical information about the patient's participation, and should be scheduled preferably before there has been a substantial lapse in study medication usage. However, even if there has been a medication lapse, the patient should be encouraged to return to the clinic for this visit, and should be instructed to return all remaining study medication.

The following assessments and procedures are completed at this visit in the following general order:

- Collect returned study medication from patient and perform drug accountability
- Assess study drug compliance
- Assess for occurrence of AEs

- Assess for changes in concomitant medications
- Obtain vital signs including weight
- Draw blood for clinical laboratory tests
- For women of child-bearing potential, conduct urine pregnancy test
- Inspect the oral cavity and document findings, if any
- Have the patient complete the PROMIS-Sleep Disturbance Scale and SDS
- Have the patient complete the BDI-II
- Conduct the C-SSRS after reviewing the results of the BDI-II
- Conduct CGI-I comparing to the P306 baseline

Once these assessments have been completed, the patient may be discharged from the study, provided there is no need for additional follow-up to continue to monitor an AE or other condition.

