## 10.4.1.5. Clinical Laboratory Assessments

The clinical laboratory evaluations to be performed in this study are listed in Table 2. All tests will be performed at Baseline/Visit 1 (or the Week 12 Visit of the 12-week open label HONOR study), after 28 weeks (Visit 5) and after 40 weeks of treatment (Visit 6) for Track A patients, or after 52 weeks of treatment (Visit 7) for Track B patients, or ET.

With the exception of the urine pregnancy tests, all clinical laboratory evaluations will be analyzed via a central clinical laboratory, and information regarding appropriate sample volume, collection tubes, sample labeling and handling, and shipment will be provided in a study manual. Each clinically significant abnormal laboratory value or other clinically meaningful abnormality should be followed until the abnormality resolves or until a decision is made that it is not likely to resolve. If such abnormalities do not return to normal within a reasonable period, their etiology should be identified and Tonix or designee should be notified. Treatment-emergent clinically significant abnormalities in laboratory values will be recorded as AEs.

**Table 2:** Clinical Laboratory Assessments

Clinical chemistry	Hematology
Alanine aminotransferase (ALT)	Hematocrit

Alkaline phosphatase	Hemoglobin
Aspartate aminotransferase (AST)	MCH concentration (MCHC)
Bilirubin (total)	Mean corpuscular hemoglobin (MCH)
Blood urea nitrogen (BUN)	Mean corpuscular volume (MCV)
Calcium	Platelet count
Chloride	Red blood cell (RBC) count
Cholesterol (total)	White blood cell (WBC) count differential
Creatinine kinase (CK)	Neutrophil count (absolute and %)
Creatinine	Lymphocyte count (absolute and %)
Glucose	Monocyte count (absolute and %)
Phosphorus	Eosinophil count (absolute and %)
Potassium	Basophil count (absolute and %)
Protein (albumin and total)	WBC count
Sodium	
Urine Pregnancy Test (qualitative dipstick) a	
Pharmacogenomic testing (optional; can be obtained at any visit, including an early termination visit)	

<sup>a Pregnancy testing for females of child-bearing potential only. A positive pregnancy test mandates withdrawal from the study (all visits).

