7.1.1 Adjustments for Multiplicity and Other Alpha Control

7.1.1.1 Multiplicity

No adjustments will be made from multiplicity and all p-values will be nominal.

7.1.2 Data Handling for Participants Who Discontinue Study Drug or Withdraw from the Study

Participants who withdraw/drop out from the study will have their ET visit data collected and included in the analysis based on the closest visit window (Week 7, 16, 28, 40, or 52). Visit windows will be assigned by splitting the periods between visits at the midpoint between the visits. If more than one record falls within the window, the one closest to the target date will be used in the analysis, with preference given to the scheduled visits in the case of equidistant visits.

Protocol: TNX-CY-P306 Page 15 of 36

Final v1.0

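### SAP 10.2 and 10.4 place early-termination laboratory and vital-sign values at the nearest empty visit with no distance limit, in conflict with the window rule in SAP 7.1.2

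*SAP*

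**What the plan says.** SAP 10.2 (laboratory) and SAP 10.4 (vital signs, including weight) carry the same sentence: "ET data will be analyzed with the closest visit that does not have a valid assessment value". Neither gives a window or a maximum distance.

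SAP 7.1.2, in the general methods, sets a different rule. ET data go to the nearest of the windows around Weeks 7, 16, 28, 40 and 52. The boundaries are defined: "Visit windows will be assigned by splitting the periods between visits at the midpoint between the visits". Duplicates are resolved within the window: "If more than one record falls within the window, the one closest to the target date will be used in the analysis".

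The schedules differ by assessment. Protocol 10.4.1.4 has vital signs at every in-clinic visit. Protocol 10.4.1.5 has post-baseline laboratory tests only "after 28 weeks (Visit 5) and after 40 weeks of treatment (Visit 6) for Track A patients, or after 52 weeks" for Track B, or at ET. Protocol 9.3 confirms that, among Weeks 7, 16 and 28, blood is drawn only at Week 28. The ET visit in Protocol 9.6 includes "Draw blood for clinical laboratory tests" whenever it occurs.

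SAP 10.2 reports laboratory values and changes by visit, with 95% CIs and shift tables. SAP 10.4 reports vital signs by assessment time with 95% CIs, and adds a last on-treatment summary.

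**The concern.** Visits already attended hold valid values. For a patient who has missed nothing, the only empty visits lie ahead, so the ET value is reported at a visit the patient never reached. The row label then overstates exposure. A change that builds up with exposure is diluted in later rows, and an early abnormality that led to withdrawal can appear in the shift table as a late one.

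The two rules can also put the same patient's value in different rows, or use it under one rule and not the other. Two programmers following the SAP could produce different tables. Long-term safety is the primary objective, so the time label on these rows matters.

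**Working it through.** **Inputs.** Target days 49, 112, 196, 280 and 365 (Protocol Appendix 1, each ±7 days), with Day 365 for Track B only. Assessment schedules as above. The documents give no dropout rate or timing. Assumed throughout: no missed earlier visits and scheduled visits on target. For averages, withdrawal is also assumed uniform over 40 weeks (Track A) or 52 weeks (Track B).

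**1. Windows under 7.1.2.** Midpoints: (49+112)/2 = 80.5; (112+196)/2 = 154; (196+280)/2 = 238; (280+365)/2 = 322.5. Week 28 therefore takes Days 154 to 238, or Weeks 22 to 34.

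**2. The rules side by side.**

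| ET value | SAP 7.1.2 | SAP 10.2 / 10.4 | Days moved by 10.2 / 10.4 |
|---|---|---|---|
| Vital signs, Day 21 | Week 7 | Week 7 | 28 |
| Vital signs, Day 60, Week 7 attended | Week 7 window; ET record not used | Week 16 | 52 |
| Vital signs, Day 203 (Week 29), Week 28 attended | Week 28 window; ET record not used | Week 40 | 77 |
| Laboratory, Day 21, scheduled-draw visits eligible | Week 7 | Week 28 | 175 |
| Laboratory, Day 21, all clinic visits eligible | Week 7 | Week 7 | 28 |
| Laboratory, Track B, Day 200, valid Week 28, scheduled-draw visits eligible | Week 28 window; ET record not used | Week 52 | 165 |
| Same, all clinic visits eligible | Week 28 window; ET record not used | Week 40 (no Track B draw there) | 80 |

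The largest shift over all possible ET days is 83 days (Track A) or 84 days (Track B) for vital signs. It is 195 days for laboratory tests with scheduled-draw visits eligible.

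**3. Average shift.** The nearest empty visit is the next one, so with gaps L between eligible visits and total T, the mean shift is ΣL²/(2T).
- Vital signs, A: (7²+9²+12²+12²)/80 = 418/80 = 5.2 weeks.
- Vital signs, B: (418+12²)/104 = 562/104 = 5.4 weeks.
- Laboratory, scheduled-draw visits, A: (28²+12²)/80 = 928/80 = 11.6 weeks.
- Laboratory, scheduled-draw visits, B: (28²+24²)/104 = 1360/104 = 13.1 weeks.

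If all clinic visits are eligible for laboratory tests, every ET sample before Week 22 goes to Week 7 or 16: 22/40 = 55% (A) or 22/52 = 42% (B) of ET samples.

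**4. How often the rules disagree.** Running every possible ET day, excluding the target days themselves: vital signs 115 of 276 days (42%) in Track A and 157 of 360 (44%) in Track B; laboratory tests, scheduled-draw visits, 194 of 276 (70%) and 277 of 360 (77%). These are shares of calendar days, not of patients.

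**5. Understatement at Week 28 of a change proportional to exposure.** Let a fraction p leave before Week 28, uniformly, all assessed at ET.
- Laboratory, scheduled-draw visits: all leavers are labelled Week 28, with mean true time Week 14. Understatement = 1 − [(1−p) + p×14/28] = p/2, giving 5, 10, 15 and 20% for p = 10, 20, 30 and 40%.
- Weight: only leavers from Weeks 16 to 28 (12/28 of p) are labelled Week 28, with mean true time Week 22. Understatement = [(12/28)p / ((1−p) + (12/28)p)] × 6/28. For p = 40%: 0.171/0.771 × 6/28 = 4.8%. For p = 10, 20 and 30%: 1.0, 2.1 and 3.3%.

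**The case against.** **Specific over general.** Sections 10.2 and 10.4 can be read as assessment-specific rules that override 7.1.2, chosen to keep ET values that 7.1.2 would not use when a closer record shares the window. That is a reasonable safety motive. But the SAP does not state the override; only Section 12 says its definitions may differ from other sections, and Section 13 is silent. Settling precedence would still leave no distance limit.

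**Dependence on one reading.** A reader might infer that a Week 3 laboratory sample is certain to be reported as Week 28. That holds only if eligible visits are those with a scheduled draw. It is the more natural reading, since the shift tables use scheduled time points, but the SAP does not say so. Rule 7.1.2 alone would also put that sample in a Week 7 window with no planned laboratory test, so dropout-only rows are not peculiar to 10.2.

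**Limited reach.** A reader might infer that the long-term safety conclusions as a whole are distorted. The documents do not support that. Listings, the last on-treatment summary in 10.4, and the Section 12 minimum, maximum, final-value, worst-shift and liver-category analyses do not use visit labels. Clinically significant treatment-emergent laboratory abnormalities are also recorded as AEs with their own onset date (Protocol 10.4.1, 10.4.1.5). This objection stands, and it limits the point to descriptive tables.

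**Conclusion.** The point holds for the by-visit laboratory and vital-sign summaries, their 95% CIs and the laboratory shift tables. The conflict between rules and the missing distance limit are plain from the text and need no assumption about dropout.

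For vital signs the forward shift is at most 12 weeks and about 5 on average under uniform withdrawal. For laboratory tests it is up to 28 weeks and averages 11.6 to 13.1 weeks, but only if scheduled-draw visits alone are eligible.

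The 5-20% understatement should not be read across to weight, where the same assumptions give about 1-5%. Even for laboratory tests it is an upper-end illustration. It assumes that every leaver gives an ET sample, whereas Protocol 9.6 only has patients instructed to attend, and that change is linear in exposure. This is worth correcting because the time labels are wrong and the correction is cheap; it does not put the Section 12 results in doubt.

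**What to change.** Delete the ET sentence from SAP 10.2 and 10.4. Use an ET value in a by-visit row only if all three conditions hold:

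1. The assessment is scheduled at that visit for the patient's track.
2. The ET date lies in that visit's 7.1.2 window, using the existing all-visit boundaries (Days 80.5, 154, 238 and 322.5).
3. No scheduled value exists in that window.

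Do not rebuild wider windows on the laboratory schedule. SAP 7.1.2 gives the first window no lower limit, so a laboratory-only Week 28 window could still take a Week 3 sample. If baseline counted as a visit, it could still take samples from Week 14 on.

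Report all ET values in a separate Early Termination row with actual study week. Include them in a last on-treatment row for both assessments; 10.4 already plans one for vital signs, 10.2 does not. A Week 3 laboratory sample would then appear only in those two rows.

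The cost is two SAP edits, one or two extra table rows and a slightly smaller by-visit n. No new data are needed, and no ET value is lost.
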